## 1.0 PROTOCOL SUMMARY AND/OR SCHEMA

This is a 2-stage feasibility study of the non-invasive detection of tumor hypoxia using fluorine-18-labeled fluoro-misonidazole (F-FMISO), a PET tracer of hypoxia. The primary objective is to determine the feasibility of a non-invasive method of detecting hypoxia, F-FMISO-PET imaging, in colorectal cancer patients, with feasibility defined as the ability to identify regions of interest (ROI) on the F-FMISO scan that distinguish hypoxic versus normoxic regions in colorectal tumors.

Please note that all patients entered on this protocol will undergo the standard of care for their disease site. The information obtained from the use of F-FMISO PET scans will NOT be used to guide patients' treatment on this protocol.

This study is being performed under the FDA's Radioactive Drug Research Committee (RDRC) program.

## Schema:

- 1.1 Evaluation and consent.
- 1.2 A CT scout and attenuation scan will be performed on a combination PET/CT scanner to identify and localize the tumor at the center of the 15 cm PET scanner field of view. The patient will be injected while in the scan position with the F-FMISO hypoxia-specific radiotracer. Simultaneous with the injection, a dynamic PET will be initiated, to collect radiotracer pharmacokinetic information.
- 1.3 The dynamic PET image frames will be used to analyze the hypoxia-specific radiotracer uptake and assist in determining the distribution of tumor hypoxia.
- 1.4 Digital autoradiography will be performed on the resected specimen in patients who undergo surgery on the same day as the F-FMISO PET.

## 2.0 OBJECTIVE AND SCIENTIFIC AIMS

Our primary objective is to determine the feasibility of a non-invasive method of detecting hypoxia, using F-FMISO-PET imaging in colorectal cancer patients. Feasibility is defined as the ability to identify regions of interest (ROI) on the F-FMISO-PET images that distinguish between hypoxic and normoxic regions within colorectal tumors.

Secondary objectives include determining the volume of hypoxic tumor ROIs as a proportion of the entire tumor volume by this non-invasive imaging technique. ROIs are defined as those voxels, within the tumor volume defined on FDG PET/CT, for which the F-FMISO radioactivity concentration is greater than 1.2 times that

measured in blood. Selection of this threshold is based on the largest body of F-FMISO studies in humans (20, 21).

We will also obtain pharmacokinetic data on the biodistribution of F-FMISO in patients with colorectal cancer to determine the optimal interval between drug administration and PET imaging.

Digital autoradiography, when performed, will allow us to determine the correspondence between the micro-distribution of F-FMISO and the tumor histology.

## 3.0 BACKGROUND AND RATIONALE

# 3.1 Hypoxia

Hypoxia is a characteristic feature of malignant solid tumors that has been well established (1,2). Unlike healthy tissues, many tumors contain a fraction of hypoxic cells, which immunohistochemical studies suggest consist of areas of up to several hundred microns in diameter that are poorly perfused (3). It is well known that hypoxia renders tumor cells up to three times more resistant to ionizing radiation than aerobic cells (1-3). In addition to increased radioresistance, hypoxia is associated with a more aggressive phenotype and increased metastatic potential (4,5). It has also been shown in several studies to be an important determinant of loco-regional control of head and neck tumors (6,7).

A large amount of direct and indirect evidence also supports the presence of a significant hypoxic fraction in human rectal cancer. Hemoglobin saturation of red blood cells within microvessels averaged 43% in rectal cancer biopsies vs. 80% in the corresponding biopsies of normal rectal mucosa (8). Direct *in vivo* pO2 measurement with polarographic electrodes in human rectal cancer have revealed a mean pO2 of 20-30 mm Hg (8-11), with 23-45% of all measured values below 10 mm Hg (10,11). Also noted in these studies is the marked heterogeneity of oxygenation in rectal tumors. This heterogeneity may explain the wide extent of rectal cancer response to preoperative combined modality therapy (12).

There is mounting evidence that hypoxia is not only a potentially important prognostic factor in patients with rectal cancer, but in colon cancer patients as well. Studies utilizing immunohistochemical techniques have identified certain proteins, up-regulated during hypoxic conditions, correlate with increased rates of lymph node and distant metastasis (30), tumor recurrence and overall survival (31,32). This data suggests that hypoxic tumors may behave more aggressively than normoxic tumors.

As hypoxia is a known cause of radioresistance (1-3)(particularly important with regard to tumors that are treated with radiation therapy, such as locally advanced or recurrent rectal cancers and head & neck cancers), a number of methods aimed at improving tumor oxygenation are currently under investigation (ie. hyperbaric oxygen therapy (33), carbogen breathing (34) or administration of vasoactive agents (35)). Currently, the most extensively studied method includes administration of radiosensitizing agents (eg. Tirapazamine) concurrently with radiotherapy (36).

Tirapazamine, a hypoxic cytotoxin, preferentially targets hypoxic cells and induces DNA double strand breaks, leading to cell death. As demonstrated in head and neck cancer, cancer of the uterine cervix and non small cell lung cancer, tirapazamine holds promise as both a radiosensitizer and has synergistic chemotherapeutic effect when combined with cisplatin. This drug has been studied here at MSKCC in patients with cervical and non-small cell lung cancer (IRB Protocols 94-082, 94-114, 96-062), and is currently under investigation as an adjunct in patients undergoing chemoradiotherapy for cervical cancer (IRB Protocol 07-128).

If we are able to demonstrate that colon cancers contain a significant hypoxic fraction, we can justify the study of tirapazamine (or similar compounds) in patients with colorectal cancer. Currently, oxaliplatin is both highly active and widely used in the treatment of colon cancer patients. If active these patients, tirapazamine, in conjunction with oxaliplatin, may prove more efficacious than current chemotherapeutic regimens.

[figure not shown]
PET is a noninvasive imaging modality with the potential to identify tumor hypoxia through the use of hypoxia-targeting radiotracers. If these hypoxic regions are identified, they (a) may translate into a new prognostic indicator of therapeutic outcome and (b) be specifically targeted with additional radiation and perhaps translate into further improvement in local control.

## 3.2 F-FMISO PET

F-FMISO PET is a recently developed imaging modality useful in detecting and quantifying hypoxic regions within tumors. This tool has been studied both *in vitro* and *in vivo* across a wide range of human tumor types. While it is well established that polarographic needle electrode assessment of tissue oxygen tension is considered the "gold standard" for detecting and measuring degree of hypoxia, we continue to investigate new, less invasive techniques. A number of studies comparing F-FMISO PET imaging to needle electrode measurements in advanced head and neck tumors and soft tissue sarcomas have validated its use in studying hypoxia (13, 29)

Radiolabeled nitroimidazoles (including F-FMISO) have emerged as useful non-invasive markers of hypoxia. These molecules, in their native form, are lipophilic and freely diffusible across cell membranes. Once intracellular, they undergo an

enzymatic reduction reaction. In the presence of oxygen, this reaction is rapidly reversed and the molecule is free to diffuse out of the cell, obtaining transmembrane equilibrium. In a hypoxic environment, the reduced molecule covalently binds to intracellular macromolecules, effectively trapping it within the cell (20, 28).

At our institution, in a rat prostate cancer tumor model, as well as in two colorectal cancer xenograft models, F-FMISO microPET imaging has been used to detect tumor hypoxia. These results were corroborated by measuring pO2 directly using the OxyLite probe system (14). Preliminary results support the feasibility of imaging hypoxic subvolumes in some tumors, and we propose its use in studying colorectal tumors.

## 3.3 PET Studies

PET studies using hypoxic markers have also been performed in patients both at other centers as well as at MSKCC. For example, Rasey, et al. has demonstrated the efficacy of PET imaging with F-FMISO in quantifying hypoxia in both head and neck and lung cancer patients (13). Hypoxia was observed in 97% of the tumors studied with F-FMISO PET imaging, and median fractional hypoxic volumes of 48% for lung cancer and 9% for head and neck cancer were detected. The extent of hypoxia varied markedly between tumors of the same site or of the same histology. Hypoxia was also distributed non-uniformly between regions within a given tumor.

Eschmann, et al. suggests that the efficacy of radiotherapy can be predicted on the basis of the kinetic behavior of F-FMISO in tumors of head and neck and non-small cell lung cancer (15). [name], in the Dept. of Radiation Oncology at MSKCC, has successfully completed a study of 20 head and neck cancer patients using F-FMISO PET, in which 18/20 showed F-FMISO tumor uptake (16). In

this protocol, we propose to investigate F-FMISO PET imaging in patients with colorectal cancer.

#### 3.4 Trials

A phase I trial of concurrent tirapazamine, a hypoxic cell sensitizer, cisplatin, and radiotherapy in the treatment of advanced head and neck cancer has been completed at the Peter MacCallum Cancer Institute in Australia (17). All patients underwent F-FMISO PET to demonstrate tumor hypoxia. All patients also had baseline FDG PET scans and the F-FMISO and FDG scans were co-registered. F-FMISO PET scans in this study were obtained two hours after radiotracer administration. All PET imaging was performed on a dedicated PET scanner with the data processed using measured attenuation correction and iterative reconstruction. Fourteen out of the fifteen patients had detectable hypoxia on baseline F-FMISO scan with focal abnormality corresponding to a region of increased FDG uptake in either the primary lesion or the nodal mass. In all cases, the intensity of F-FMISO uptake was less than the corresponding FDG abnormality. On the co-registered PET images, necrotic regions, as evidenced by central photopenia on FDG PET, demonstrated F-FMISO distribution only at the inner border of FDG uptake. In those regions without necrosis on FDG PET, only the central part of the metabolically active lesion had F-FMISO retention. The pattern of F-FMISO uptake was consistent with the expected pattern of hypoxia in tumor tissue being adjacent to areas of tumor necrosis or in the center of non-necrotic lesions. The rapid normalization (i.e. reduction in tumor uptake) of F-FMISO PET scans suggests successful treatment of the hypoxic component.

In another phase I trial, also done at the Peter MacCallum Cancer Institute in Australia (18), patients with inoperable rectal cancer or symptomatic primary rectal cancer with metastasis were given oxaliplatin on day 1 of weeks 1, 3 and 5 of radiotherapy. Dose level 1 was oxaliplatin 70 mg m^-2 with 5-FU 200 mg m^-2 day continuous infusion 96 h week. On dose level 2, the oxaliplatin dose was increased to 85 mg m^-2. On dose level 3, the duration of the 5-FU was increased to 168 h week. Pelvic radiotherapy was 45 Gray (Gy) in 25 fractions over 5 weeks with a boost of 5.4 Gy. FDG- and F-FMISO-PET were used to assess metabolic tumor response and hypoxia. In total, 16 patients were accrued. Dose-limiting toxicities occurred in one patient at level 2 (grade 3 chest infection), and two patients at level 3 (grade 3 diarrhea). Dose level 2 was declared the recommended dose level. FDG-PET imaging showed metabolic responses in 11 of the 12 primary tumors assessed. Four of six tumors had detectable hypoxia on F-FMISO scans.

A prospective study from Germany (22) on 103 patients with locally advanced cancer of the uterine cervix demonstrated that tumor oxygenation, measured with a standardized polarographic method, is a strong pre-therapeutic prognostic factor. Patients with hypoxic tumors had a significantly worse disease-free and

overall survival following surgery alone, mainly due to locoregional failures with or without distant metastases.

## 3.5 Summary

Hypoxia is a characteristic feature of malignant solid tumors associated with poor prognosis and resistance to chemotherapy and radiation. It has also been shown (6) that the presence of hypoxia may reduce long-term survival post surgery. Hypoxia renders tumor cells up to three times more resistant to ionizing radiation than aerobic cells. The presence of hypoxic regions within tumors may be one factor leading to local failure after treatment with standard pre-operative radiotherapy doses. If these regions could be identified and verified using a non-invasive imaging technique prior to surgery, they could be specifically targeted using sophisticated planning techniques such as intensity modulated radiation therapy (IMRT) to deliver higher doses ionizing radiation with pre-operative radiotherapy. Future studies using IMRT to "dose paint" areas of hypoxia within tumors will build upon the results of this feasibility study. Ultimately, by the delivery of differential dose of radiation to the tumor, in combination with surgery, the local control rates of rectal cancer patients may further be improved.

## 4.0 OVERVIEW OF STUDY DESIGN AND INTERVENTION

## 4.1 Design

All patients will undergo the standard of care for their colorectal cancer and will have an FDG PET/CT scan performed within six weeks of a dynamic F-FMISO PET/CT scan. We will accept FDG PET scans not performed at MSKCC if the outside study was performed as a dedicated PET/CT and the full data set (including all CT and PET images) is submitted digitally to us accompanied by a report clearly indicating the administered activity, uptake time and blood glucose level at the time of the study. The patient will receive no treatment between the two scans. Both scans will be performed before radiochemotherapy. The FDG PET scan will be used to delineate the tumor volume. The accompanying CT of both FDG and F-FMISO will be co-registered, to allow selection of the F-FMISO intra-tumoral hypoxic voxels.

Regions of interest (ROI) corresponding to hypoxic tumor sub-volumes will be defined as those voxels, within the tumor volume defined on FDG PET/CT, for which the F-FMISO radioactivity concentration is greater than 1.2 times that measured in blood. The selection of this threshold is in concordance with the largest body of F-FMISO studies in man (20, 21), which were successfully adopted in our own studies in head and neck cancers by [name].

This is a feasibility trial using a 2-stage design. In the first stage, 15 patients will receive an F-FMISO PET scan. If 4 or fewer patients have ROIs, the study will be stopped but if 5 or more patients have ROIs then an additional 15 patients at most will be scanned. We will therefore scan a maximum of 30 patients in order

to determine the hypoxia fraction in colorectal cancer using F-FMISO. We anticipate the need to enroll approximately 50 patients to account for withdrawals of consent or inability of subjects to complete protocol requirement in order to achieve our target of 30 completed scans. Once this has been established, we propose a larger trial in order to correlate hypoxia fraction with treatment outcome.

Digital autoradiography will be performed on frozen tumor tissue sections obtained from the resected specimen in patients who undergo surgery on the same day as the F-FMISO PET in order to determine the micro-distribution of F-FMISO (see details in Section 4.2, "Intervention").

## 4.2 Intervention

# F-FMISO PET scan

Dynamic PET scans will be performed on one of the GE Discovery PET/CT scanners in 2D mode. The patient will be set up in the radiotherapy treatment position with intra-venous lines for radiotracer injection and for venous blood sampling. A CT scan of a 15cm segment of the body (the field of view of the PET scanner) will be performed with the tumor at the field center. These images will be used for both attenuation correction and registration of the serial image set.

Immediately thereafter, a single 370 MBq (10 mCi) dose of F-MISO will be injected as a bolus, and the dynamic scan initiated coincident with the injection. Data will be acquired in 1-minute time intervals continuously from 0-30 minutes. The patient will then be removed from the scanner. Since no further F-FMISO will be injected in the patient, there will be no further radiation exposure from radiopharmaceutical. The 2nd PET scan (optional and performed at 90 minutes) and the 3rd PET scan (non-optional and performed between 120-240 minutes) will each consist of a 10-minute image of the tumor consisting of two consecutive 5minute time frames. A 15-cm body segment low dose CT scan will be performed at each of these two additional image sessions for attenuation correction and image registration. The radiation dose of the first CT scan will be 0.9 mCi and the dose for the 2nd (optional) and 3rd (non-optional) scans will be 0.1 mCi each, for a total exposure of 1.0-1.1 mCi for all 3 CT scans. This total dose is approximately equivalent to one half (1/2) of the radiation exposure from a single diagnostic CT scan. To further improve patient image registration, the patient will have markers placed on the skin, inferior and superior to the lesion, to facilitate accurate laser set-up for the subsequent 2nd (optional) and 3rd (nonoptional) scans.

Note that the patient will receive the radiation dose from only one F-FMISO injection and from 2-3 low-dose CT scans. For a detailed estimate of radiation absorbed doses to organs as a result of these scans, please refer to Table 1.

# Blood pharmacokinetic sampling

For pharmacokinetic modeling, the dynamic data of the F-MISO radiotracer in the tumor must be supplemented by clearance data from the blood. This data will be ascertained by ROI analysis on an artery defined on the PET images. A limited number of blood samples (up to a maximum of 3) will be drawn (if possible) for the purpose of calibrating the image ROI data. When blood samples are taken, they shall be acquired at pre-designated times in conjunction with the PET scan from a single I.V. line inserted into the patient prior to the procedure. One blood sample will be taken per imaging time point, for a total of 2-3 blood samples. Between 1 and 3 cc of blood will be removed at each time point (making the maximum volume of blood withdrawn during this study < 9 cc).

These samples will be weighed and counted on a sensitive well scintillation counter in the nuclear medicine clinic by skilled nuclear medicine laboratory personnel for the purpose of an accurate determination of the amount of radioactive tracer in the blood versus time. The blood sample data will allow tumor-to-blood ratios to be determined for each of the imaging time points and provide information on the evolution of radiotracer entrapment within the hypoxic tumor regions. The kinetics of tumor uptake and blood clearance will be used to determine the optimal time to perform the F-FMISO scan. Once pharmacokinetic modeling is complete, blood sampling will be discontinued. Therefore, not all 30 patients who undergo F-FMISO scans will necessarily have blood sampling during imaging.

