## 9.0 TREATMENT/INTERVENTION PLAN

Within six weeks of the FDG PET scan, patients will undergo an F-FMISO PET scan. Patients will receive no treatment between the two scans. The F-FMISO scan will be conducted as follows:

- An I.V. line will be placed in each of the left and right forearms (i.e., a total of 2 I.V. lines). One line will be used exclusively for radiotracer injection and the other exclusively for blood sampling (see below).
- A scout view, followed by a low-dose CT of the tumor region will be obtained.
- The couch will automatically advance into the PET detector component of the scanner so that the tumor is in the center of the 15 cm PET field of view.
- The patient will be injected intravenously with 370 MBq (10 mCi) of F-FMISO, simultaneously with the start of PET image acquisition.
- Dynamic images consisting of five 1-minute images and five 5-minutes images (duration 30-minutes) will be acquired within one 15 cm field of view.
- Patient will be taken out of the scanner.
- Patient will undergo a 2nd (optional) PET scan at 90 minutes and a 3rd (non-optional) PET scan at 120-240 minutes post-injection. These scans will consist of a 10-minute PET acquisition and a low-dose CT.
- When blood sampling is required, up to a maximum of 3 blood samples will be obtained using the second I.V. line immediately at selected times post-injection and during the PET scan procedure. Samples will be taken with each imaging time point. Between 1 and 3 cc of blood will be removed at each time point (making the maximum volume of blood withdrawn during this study < 9 cc).

• .

- These samples will be weighed and counted in the Nuclear Medicine laboratory for the purpose of determining the blood clearance kinetics and the tumor input function.
- At the end of the entire study, the I.V. lines will be removed.
- The radiopharmacy will keep a log of all injected activity. All patient doses are permanently recorded in the Nuclear Pharmacy database. The injected F-FMISO dose, injection time and scan time are also recorded in the PET image file header, and can be accessed from the PET images themselves.
- Digital autoradiography will be performed on up to two tissue samples from patients who undergo surgery on the same day as the F-FMISO scan (see details in Section 4.2, "Intervention").

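### Does stopping the blood samples leave some patients without a blood value for the 1.2 tumor-to-blood ratio behind the 13-of-30 rule?

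*Combined protocol and SAP*

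**What the plan says.** Sections 2.0 and 4.1 define a hypoxic region as tumor voxels with an FMISO concentration above 1.2 times that in blood. Section 14.0 applies a ratio of at least 1.2 at one late time point, adds a kinetic-profile criterion, and uses both kinds of data to call a scan positive. Positive scans are counted against 5 of 15 and then 13 of 30.

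Section 4.2, under Blood pharmacokinetic sampling, describes two blood measurements.

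- Image-based. Of the blood clearance data it says: "This data will be ascertained by ROI analysis on an artery defined on the PET images". Up to three samples "will be drawn (if possible) for the purpose of calibrating the image ROI data".
- Counted samples. These are venous: the patient is set up "with intra-venous lines for radiotracer injection and for venous blood sampling". They are counted "for the purpose of an accurate determination of the amount of radioactive tracer in the blood versus time", and "The blood sample data will allow tumor-to-blood ratios to be determined for each of the imaging time points".

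The section then says: "Once pharmacokinetic modeling is complete, blood sampling will be discontinued". It adds that not all 30 patients who undergo FMISO "scans will necessarily have blood sampling during imaging". Section 9.0 is also conditional: "When blood sampling is required, up to a maximum of 3 blood samples will be obtained using the second I.V. line". It gives the purpose of the samples as blood clearance kinetics and the tumor input function.

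**The concern.** The only sentence that names a source for tumor-to-blood ratios names the counted samples, and the same paragraph says some patients will have none. The primary count needs a ratio in all 30. If both criteria in section 14.0 must be met, every positive call needs the ratio; if either is enough, every negative call does.

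The artery region could supply the missing value, but it is introduced for pharmacokinetic modeling. No sentence says that it is the denominator of the 1.2 ratio, or how it is calibrated in a patient without samples. If sampled patients were read against venous counts and the rest against an arterial image value, a steady difference between the two would move the cut-off in one group only. The stated error rates assume one definition of a positive scan in all 30. The secondary estimate of hypoxic volume uses the same threshold.

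**Working it through.** **1. The plan's own figures.** Inputs from section 14.0: 15 patients in stage 1, stop at 4 or fewer; 15 more; success at 13 or more of 30; 30% too low, 50% desirable. With X1 and X2 each Binomial(15, p),

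P(success) = sum over x = 5 to 15 of P(X1 = x) × P(X2 ≥ 13 − x).

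- p = 0.30: 0.0805 (stated 8%).
- p = 0.50: 0.8043 (stated 80.4%).

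Both stated figures reproduce. They need the same definition of a positive scan in every patient, and nothing more about blood.

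**2. The text side by side.**

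- The sentence about ratios refers to each imaging time point. It goes on to tracer trapping over time, and the next sentence concerns the best time to scan. That is the pharmacokinetic objective of section 2.0. The primary criterion uses a single late time point.
- Section 9.0 gives the samples the same kinetic purpose. Ending them when the modeling is finished is consistent with it.
- The sentence says what the samples make possible. It does not say that ratios can come from nowhere else.
- The artery region exists wherever there is a scan, and the late scan is mandatory. A counted sample cannot be the denominator for all 30, because the plan expects some patients to have none. Only the image value can serve everyone.

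**3. How often one patient decides the verdict.** This needs no assumption about blood error. It concerns the final count in trials that pass stage 1. Write S(r) for the probability of passing stage 1 and reaching at least r of 30.

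- A false success from one wrongly positive patient needs a true count of 12. At p = 0.30: S(12) − S(13) = 0.1454 − 0.0805 = 0.0650 (from unrounded values), or 6.5%.
- A lost success from one wrongly negative patient needs a true count of 13. At p = 0.50: S(13) − S(14) = 0.8043 − 0.7005 = 0.1038, or 10.4%.

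Any count threshold has such a margin. These figures do not show that any patient is misread.

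**4. Illustrations of blood error.** The documents give no error size, spread or number sampled. Assumed here: the ratio alone decides; it is normal with SD 0.3 and a mean set so that 30% or 50% exceed 1.2; the last 15 patients have no samples.

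*(a) One common calibration carried forward, random patient-level error cv.* The positive rate in the last 15 is P(N(mean, √(0.3² + (1.2·cv)²)) > 1.2).

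| cv | False success (p = 0.30) | Power (p = 0.50) |
|---|---|---|
| 5% | 8.4% | 80.4% |
| 10% | 9.2% | 80.4% |
| 15% | 10.5% | 80.4% |

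Adding the uncertainty of a factor estimated from 15 sampled patients gives false success of 8.5%, 9.6% and 11.2%, and power of 80.3%, 79.9% and 79.4%. With a factor from only 5 patients and 25 read on it, the figures are 9.6%, 13.7% and 18.9%, and 79.3%, 77.0% and 74.6%.

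*(b) Two different blood values with an uncorrected 5% offset in the last 15.*

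- Blood reads low: the cut-off becomes 1.2 × 0.95 = 1.14, the positive rate rises from 30% to 37.3%, and false success is 15.7% (20.6% to 10.5% over SD 0.2 to 0.8).
- Blood reads high: the cut-off becomes 1.2 × 1.05 = 1.26, the positive rate falls from 50% to 42.1%, and power is 67.7% (60.1% to 76.2%).
- At the 70% the team thinks possible, the high offset leaves the chance of success at 99.4% to 99.8%, against 99.9% without it.

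**The case for a change.** The strongest case for a change is that the denominator of the primary endpoint should not be left to inference. The one sentence on ratios names the samples, venous counts and an arterial image value need not agree, and a calibration made patient by patient is impossible without samples. The size of the group behind any common factor is not given, and a factor from very few patients could matter, as the five-patient figures show. One sentence would settle it at no cost in scans or draws.

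Part of this stands. The plan nowhere names the denominator or the calibration for an unsampled patient, and no redaction explains the omission. The rest is weaker. The largest effects, in 4(b), assume that the image value is never corrected, although the samples are drawn to correct it. The five-patient case has no source in the documents. Every illustration lets the ratio alone decide, whereas section 14.0 also uses the kinetic profile, which may limit the effect. The proposed sentence would record whichever rule the team uses; it offers no better method. Tables of agreement and of results by sampling status would add to the report without altering the count.

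**Conclusion.** The gap is real but small, and it is one of detail. On the natural reading, the image-based blood value with one common calibration serves every patient, the 13-of-30 count is sound, and the stated 8% and 80.4% stand. Stopping the samples once the modeling is complete does not conflict with the endpoint.

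This rests on the analysts treating sampled and unsampled patients alike, which is what a physicist running one software package over all scans would ordinarily do. If they did not, the effect would be of unknown size and direction; the error rates in step 4 are assumptions, not estimates. The consequence is also limited, because this is a feasibility study whose scans do not guide treatment. No change to the plan is called for.
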